- 12) Ongoing immunosuppressive therapy other than corticosteroids. ***Note: Subjects may use topical, enteric, inhaled, or systemic corticosteroids as therapy for manifestations of CLL, comorbid conditions, or autoimmune anemia and/or thrombocytopenia. During study participation, subjects may receive systemic or other corticosteroids as pretreatment for ofatumumab infusions or as needed for treatment-emergent comorbid conditions.***

- 13) In a subject with a history of prior ofatumumab therapy, the time from the last dose of ofatumumab to documented CLL progression is < 6 months.
- 14) History of prior therapy with any inhibitor of AKT, Bruton tyrosine kinase (BTK), Janus kinase (JAK), mammalian target of rapamycin (mTOR), phosphatidylinositol 3-kinase (PI3K) (including idelalisib), or spleen tyrosine kinase (SYK).
- 15) Prior participation in an idelalisib clinical trial.
- 16) Concurrent participation in another therapeutic clinical trial.
- 17) Prior or ongoing clinically significant illness, medical condition, surgical history, physical finding, electrocardiogram (ECG) finding, or laboratory abnormality that, in the investigator's opinion, could adversely affect the safety of the subject or impair the assessment of study results.

Study  
Procedures/  
Frequency:

Subjects will be randomized with a 2:1 ratio into Arm A or Arm B of the study. In Arm A, subjects will take idelalisib orally BID continuously and will receive 12 infusions of ofatumumab over ~24 weeks. In Arm B, subjects will receive 12 infusions of ofatumumab over ~24 weeks.

Clinic/laboratory visits will occur weekly for Weeks 1 through 8, every 4 weeks at Weeks 12, 16, 20, and 24, and every 6 weeks between Weeks 24 and 48. Subjects continuing on study drug(s) past Week 48 will have clinic visits every 12 weeks. Subjects will be assessed for safety at each visit. Subjects in Arm A will require monthly CMV testing. Subjects will be assessed for CLL disease status by physical and/or laboratory examinations at each visit and by CT or MRI at Weeks 8, 16, 24, 36, 48 and every 12 weeks thereafter until the primary endpoint is met.

---

**Test Therapy, Dose,  
and Mode of  
Administration:**

- Arm A: Idelalisib: 150 mg taken orally BID starting on Day 1 and administered continuously thereafter

---

**Study Drug, Dose,  
and Mode of  
Administration:**

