After a study drug dose reduction, the dose need not be re-escalated, even if there is minimal or no toxicity with the reduced dose. However, if the subject tolerates the lower dose level of study drug for  $\geq 4$  weeks then the dose may be increased to 150 mg BID, at the discretion of the investigator. Such re-escalation may be particularly warranted if further evaluation reveals that the adverse event that led to the dose reduction was not study-drug-related. The starting dose level should not intentionally be exceeded in this study.

Escalations or reductions in ofatumumab dosing are not planned. As noted in [Table 5-4](#), ofatumumab administrations may be delayed to allow subjects to recover from ofatumumab-related adverse events or intercurrent illness.

Whenever possible, any dose adjustment of idelalisib should be discussed between the investigator and the Gilead Sciences medical monitor prior to implementation. To implement either a dose reduction or a dose reescalation, the investigator/study staff member will access the IWRS, select the subject number, and inform the IWRS of the need for dose titration. The IWRS will provide details regarding the kit numbers to be dispensed to the subject. The appropriate clinic staff should instruct the subject/caregiver about the change in dose.

**Table 5-4. Recommendations and *Required* Actions for Idelalisib and Ofatumumab Dose Modification Based on Type and Severity of Treatment-Related Adverse Event or Laboratory Abnormality**

NCI CTCAE Grade	Recommendations and Required Action (in italics)	
	Idelalisib	Ofatumumab
HEMATOLOGICAL ADVERSE EVENTS		
Neutropenia		
Grade $\leq 2$ neutropenia	Maintain current dose level and schedule.	Maintain current dose level and schedule.
Grade $\leq 3$ neutropenia	Maintain current dose level and schedule. Blood counts must be monitored at least weekly until ANC <math>\leq</math> Grade 2.	Maintain current dose level and schedule. Consider G-CSF support.

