#### 5.4.4. Hematological and Immunological Events

In the Phase 1 experience with idelalisib in CLL, patients with Grade  $\geq 3$  neutropenia, anemia, and/or thrombocytopenia were enrolled to clinical trials. Decreased levels of neutrophil counts, hemoglobin, or platelet counts during therapy were largely due to minor fluctuations in these parameters among patients with pre-existing hematological abnormalities due to disease or prior therapy. Thus, idelalisib did not appear to induce overt myelosuppression. Obvious patterns of drug-mediated reductions in circulating CD4+ lymphocyte counts or suppression of serum IgG levels were also not observed.

Treatment-emergent Grade 3 or 4 neutropenia events, including febrile neutropenia, have occurred in subjects treated with idelalisib. All subjects should have their blood counts monitored at least every 2 weeks for the first 6 months of idelalisib treatment. For subjects who develop ANC 0.5 to  $< 1.0$  Gi/L, blood counts must be monitored weekly. For subjects who develop ANC  $< 0.5$  Gi/L, idelalisib must be interrupted and blood counts monitored weekly until ANC is  $\geq 0.5$  Gi/L, at which point, idelalisib dosing may be resumed at 100 mg BID. Neutropenia should be managed according to established clinical guidelines.

Prolonged ( $\geq 1$  week) severe neutropenia can occur with ofatumumab. Of 108 patients with normal neutrophil counts at baseline in the Phase 2 pivotal clinical trial experience {Wierda 2010}, 45 (42%) developed Grade  $\geq 3$  neutropenia and 19 (18%) developed Grade 4 neutropenia. Some patients experienced new onset Grade 4 neutropenia of  $> 2$  weeks in duration {Glaxo Group Limited 2011}. Suppression of mean serum IgG and IgA levels has not been seen. Anemia and thrombocytopenia are not as prominent.

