#### 9.4.2.5. Laboratory Evaluations

All laboratory data will be listed. Summaries of laboratory data will be based on observed data. The focus of laboratory data summarization will be on treatment-emergent laboratory abnormalities. A treatment-emergent laboratory abnormality is defined as an abnormality that, compared to baseline, worsens by  $\geq 1$  grade in the period from the first dose of study drug (idelalisib or ofatumumab) to 30 days after the last dose of study drug. If baseline data are missing, then any graded abnormality (ie, an abnormality that is Grade  $\geq 1$  in severity) will be considered treatment emergent.

Hematological, serum biochemistry, and urine data will be programmatically graded according to CTCAE severity grade, when applicable. For parameters for which a CTCAE scale does not exist, reference ranges from the central laboratory will be used to determine programmatically if a laboratory parameter is below, within, or above the normal range for the subject's age, sex, etc.

Hematological and serum biochemistry and their changes from baseline will be summarized by treatment arm, by visit, and by combination therapy vs monotherapy periods (during ofatumumab treatment vs following ofatumumab treatment). Summary tables will be presented for each relevant assay to show the number of subjects by CTCAE severity grade with corresponding percentages. For parameters for which a CTCAE scale does not exist, the frequency of subjects with values below, within, and above the normal ranges will be summarized. Subjects will be characterized only once for a given assay, based on their worst severity grade observed during a period of interest (eg, during the study or from baseline to a particular visit).

Shift tables for hematology and serum biochemistry will also be presented by showing change in CTCAE severity grade from baseline to the worst grade post baseline.

Separate listings and summaries will be prepared for laboratory abnormalities that are Grade  $\geq 3$  in severity.

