**Appendix 7. Schedule of Study Procedures**

Period	Screen	Treatment																		Follow-up	
		2	3	4	5	6	7	8	9	10	11	12	13	14	15	16	17	18+	30 day	Long-term	
Visit	1	2	3	4	5	6	7	8	9	10	11	12	13	14	15	16	17	18+	End of Study	Within +30 days	To +5 years
Week	-4	1	2	3	4	5	6	7	8	12	16	20	24	30	36	42	48	Q12 Weeks			
Study Day	Within -28 Days	1	8	15	22	29	36	43	50	78	106	134	162	204	246	288	330	End of Study	Within +30 days	To +5 years	
Visit Window			±2	±2	±2	±2	±2	±2	±2	±3	±3	±3	±3	±3	±3	±3	±3	±7			
Informed consent	X																				
Medical history	X																				
CIRS assessment	X																				
Serum virology	X																				
CMV Surveillance e						X			X	X	X	X	X	X	X	X	X	X			
PJP prophylaxis																		X g	X g		
β-HCG (women of child-bearing potential)	X	X				X			X	X	X	X	X	X	X	X	X a	X a	X		
CLL peripheral blood evaluation	X																		X		
CLL serology	X																		X		
Coagulation	X																				
Urinalysis	X																				
12-lead ECG	X																				

Period	Screen	Treatment																		Follow-up	
Visit	1	2	3	4	5	6	7	8	9	10	11	12	13	14	15	16	17	18+	End of Study	30 day	Long-term
Week	-4	1	2	3	4	5	6	7	8	12	16	20	24	30	36	42	48	Q12 Weeks		Within +30 days	To +5 years
Study Day	Within -28 Days	1	8	15	22	29	36	43	50	78	106	134	162	204	246	288	330				
Visit Window			±2	±2	±2	±2	±2	±2	±2	±3	±3	±3	±3	±3	±3	±3	±3	±7			
IWRS	X	X	X	X	X	X	X	X	X	X	X	X	X	X	X	X	X	X	X		
HRQL/ healthy utility – FACT-Leu/ EQ-5D		X	X	X	X	X	X	X	X	X	X	X	X	X	X	X	X	X	X		
Adverse events f		X	X	X	X	X	X	X	X	X	X	X	X	X	X	X	X	X	X	X	
Concomitant medications	X	X	X	X	X	X	X	X	X	X	X	X	X	X	X	X	X	X	X	X	
Performance status	X	X	X	X	X	X	X	X	X	X	X	X	X	X	X	X	X	X	X		
Oxygen saturation (by pulse oximetry)	X	X	X	X	X	X	X	X	X	X	X	X	X	X	X	X	X	X	X		
Physical exam (includes nodes, liver, spleen)	X	X				X			X	X	X	X	X	X	X	X	X	X	X		
Hematology/ serum chemistry	X	X	X	X	X	X	X	X	X	X	X	X	X	X	X	X	X	X	X		
Circulating cells/biomarkers/ serum Igs		X	X	X		X			X	X	X	X	X	X	X	X	X	X	X		
Serum CH50																		X	X		

Period	Screen	Treatment																	Follow-up		
Visit	1	2	3	4	5	6	7	8	9	10	11	12	13	14	15	16	17	18+	End of Study	30 day	Long-term
Week	-4	1	2	3	4	5	6	7	8	12	16	20	24	30	36	42	48	Q12 Weeks		Within +30 days	To +5 years
Study Day	Within -28 Days	1	8	15	22	29	36	43	50	78	106	134	162	204	246	288	330				
Visit Window			±2	±2	±2	±2	±2	±2	±2	±3	±3	±3	±3	±3	±3	±3	±3	±7			

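### After Week 8 the protocol looks for neutropenia more often in Arm A than in Arm B, so if the extra counts are analysed the by-arm worst-grade table can show a moderate Arm A excess with no drug effect

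*Protocol*

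**What the plan says.** **Monitoring tied to idelalisib.** Section 5.4.4 says: "All subjects should have their blood counts monitored at least every 2 weeks for the first 6 months of idelalisib treatment". Idelalisib is given in Arm A only. For an ANC of 0.5 to below 1.0 Gi/L the same section says that "blood counts must be monitored weekly"; that sentence names no arm. Table 5-4 (Section 5.3.4) repeats a weekly rule for Grade 3 and Grade 4 neutropenia, "Blood counts must be monitored at least weekly until ANC" is back to Grade 2 or better, and puts it in the idelalisib column. The ofatumumab column gives no count frequency.

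**Common schedule.** The Synopsis (Study Procedures/Frequency) states: "Clinic/laboratory visits will occur weekly for Weeks 1 through 8, every 4 weeks at Weeks 12, 16, 20, and 24, and every 6 weeks" up to Week 48, and every 12 weeks after that. The row "Hematology/ serum chemistry" in Appendix 7 follows these visits and does not differ by arm. Neither Appendix 7 nor the visit tables in Section 6.2 contain the 2-weekly counts.

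**Analysis rule.** Section 9.4.2.5 bases laboratory summaries on observed data, by arm, by visit, and by period during or after ofatumumab. It adds: "Subjects will be characterized only once for a given assay, based on their worst severity grade observed during a period of interest". It does not restrict the worst-grade table to scheduled visits.

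**The concern.** A worst grade is a maximum over the samples taken. More samples can only leave it unchanged or make it worse. If one arm is sampled more often, a by-arm worst-grade table compares detection as well as toxicity.

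Neutropenia is where this matters. Section 5.4.4 reports substantial Grade ≥3 neutropenia on ofatumumab alone, so the safety question is what idelalisib adds. The difference in sampling falls in Weeks 8 to 24, inside the ofatumumab period in which the arms would naturally be compared.

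There is also a second route. Section 8.1.3 makes a laboratory abnormality that leads to drug interruption a recordable adverse event, and Table 5-4 requires idelalisib interruption at Grade 4. A dip found only because of an additional Arm A count can therefore reach the adverse event and interruption tables as well.

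**Working it through.** **1. The protocol's own rates.** Section 5.4.4, ofatumumab alone, 108 patients with normal baseline counts: Grade ≥3 in 45/108 = 41.7% (stated 42%); Grade 4 in 19/108 = 17.6% (stated 18%). Both reproduce.

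**2. Number of counts.** After Day 50 through Day 162:
- Arm B: Days 78, 106, 134, 162 = 4.
- Arm A at 14-day spacing: (162 − 50)/14 = 8.
- Ratio 8/4 = 2.0. Over all post-baseline counts to Week 24, with 7 weekly counts (Weeks 2 to 8) in each arm: 15 against 11, ratio 1.36.

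**3. Detection per episode.** An episode lasting d weeks, starting at a random point and sampled every t weeks, is seen with probability min(1, d/t). Both arms have t = 1 for the first 8 weeks. For the next 16 weeks t = 2 in Arm A and t = 4 in Arm B. With a constant onset rate over 24 weeks:

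D_A = [8·min(1, d) + 16·min(1, d/2)]/24

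D_B = [8·min(1, d) + 16·min(1, d/4)]/24

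| Episode length | Weeks 8–24: A, B, ratio | Weeks 1–24: A, B, ratio |
|---|---|---|
| 1 week | 50%, 25%, 2.0 | 67%, 50%, 1.33 |
| 2 weeks | 100%, 50%, 2.0 | 100%, 67%, 1.5 |
| 3 weeks | 100%, 75%, 1.33 | 100%, 83%, 1.2 |
| 4 weeks or more | 100%, 100%, 1.0 | 100%, 100%, 1.0 |

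The 24-week ratio peaks at d = 2. Between 1 and 2 weeks it is (8 + 8d)/(8 + 4d), which rises to 24/16 = 1.5; between 2 and 4 weeks it is 24/(8 + 4d), which falls to 1.0. A simulation on the actual visit weeks gave 1.36, 1.53, 1.21 and 1.00, in agreement.

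**4. Subject level.** With Poisson episodes and equal true risk, P_A = 1 − (1 − P_B)^ratio. The protocol's rates are taken as what Arm B would show.
- P_B = 42%: 1 − 0.58^1.33 = 52%; 1 − 0.58^1.5 = 56%.
- P_B = 18%: 1 − 0.82^1.33 = 23%; 1 − 0.82^1.5 = 26%. The simulated 1-week ratio of 1.36 gives 24% for the lower end.

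For 1- to 2-week episodes the spurious excess is thus about 10 to 14 points on 42% and about 5 to 8 points on 18%.

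**5. Weekly step-up.** Weekly counts start once Grade 3 or 4 has been found, so they add nothing to a Grade ≥3 classification. They can add to Grade 4. Take a 3-week Grade ≥3 episode in Weeks 8 to 24 with Grade 4 in its middle week:
- Arm A: the first 2-weekly count falls in week 1 or week 2 of the episode. In week 2 it sees Grade 4 directly; in week 1 it triggers a recount that falls in week 2. Detection is 100% (50% without the step-up).
- Arm B: 1/4 = 25%.

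**The case against.** **Size.** From the doubled counts a reader might infer that the table would show twice as much neutropenia in Arm A. The documents do not support that. Both arms have weekly counts to Week 8, and twofold holds only for episodes of 2 weeks or less arising in Weeks 8 to 24. Section 5.4.4 describes ofatumumab neutropenia as able to last a week or longer, in some patients beyond 2 weeks. From 4 weeks the ratio is 1.0.

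**Use of the 18%.** One might multiply it by the detection probabilities to predict each arm's table. It is already an observed proportion, so it can serve only as a displayed Arm B rate, as above.

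**Strength of the rule.** The 2-weekly sentence is a recommendation, and the weekly sentence in Section 5.4.4 names no arm; the limit to Arm A comes from context and Table 5-4. The ofatumumab delay rules there also imply some repeat counts in Arm B after Grade 4. This stands and may narrow the gap.

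**Whether the counts are analysed.** The protocol does not say that counts outside Appendix 7 enter the laboratory data. If they do not, the effect of the 2-weekly rule on this table disappears. This is the most important condition on the point.

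**Existing summaries and the SAP.** By-visit summaries give a like-for-like view at common visits, no between-arm laboratory test is planned, and handling of unscheduled counts is often left to the SAP. It would therefore be too strong to say that an Arm A excess could never be interpreted. But by-visit summaries do not correct the worst-grade table, and the protocol itself sets both the unequal monitoring and the worst-grade rule.

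**Conclusion.** The point holds as a moderate, conditional bias. After Week 8 the protocol provides for about twice as many blood counts in Arm A as in Arm B through Day 162, and Section 9.4.2.5 turns observed counts into a by-arm worst grade without limiting them to common visits. If the extra counts are in the data, the per-episode Grade ≥3 detection ratio over Weeks 1 to 24 lies between 1.0 and 1.5. For episodes of 1 to 2 weeks, subject-level rates of 42% and 18% in Arm B would appear as about 52% to 56% and about 23% to 26% in Arm A with no drug effect. For Grade 4 the weekly step-up can add to this.

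These figures assume a constant onset rate, the stated episode lengths, equal true risk, full adherence to the 2-weekly recommendation, and no extra counts in Arm B. The protocol gives no distribution of episode length. The mismatch between Section 5.4.4 and Appendix 7 stands regardless of these assumptions.

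**What to change.** 1. In Section 9.4.2.5, keep the all-counts worst-grade table. Add a between-arm worst-grade table for neutrophils and other blood counts, limited to the hematology visits that Appendix 7 schedules in both arms through Visit 13, and name it as the table for comparing the arms. Its scheduled sampling ratio is 1.0.
2. Label the all-counts table, and the neutropenia adverse event and interruption tables, as affected by unequal monitoring. The added table does not repair the latter two, so the caveat is needed there.
3. Reconcile Section 5.4.4 with Appendix 7 on the 2-weekly counts, and state whether those counts enter the analysed laboratory data. Which monitoring frequency is right is a clinical matter and is not addressed here.

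Cost: one more table and some labels, with no new data or visits. The common-visit table will omit some true Arm A events; they remain in the all-counts table.

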## **6.2. Explanation of Study Visits**

The specific study procedures to be conducted for each subject enrolled in the study are presented in tabular form in [Appendix 7](#) and are described in the sections that follow. Additional information on the study procedures is provided in the study manual.

For visits at which HRQL and healthy utility data are obtained, it is important that the subject be administered the FACT-Leu and the EQ-5D before any other procedures are performed and before any study-related information is communicated to the subject; this is necessary to avoid biasing the PRO responses provided by the subject. Once the subject has completed the FACT-Leu and the EQ-5D assessments, the remaining procedures may be performed.

At visits involving idelalisib administration and pharmacokinetic sampling in the clinic, care should be taken to perform procedures with the appropriate timing relative to idelalisib administration. The actual sample collection times of pharmacokinetic blood specimens should be recorded. If a heparinized venous catheter is placed for sample collection in order to avoid repeated needle sticks, at least 2 mL of blood should be removed and discarded prior to each sample collection in order to avoid heparin contamination of the sample.

In addition to clinical assessments of tumor status, CT or MRI imaging of the neck, chest, abdomen, and pelvis will be performed as a component of tumor assessments during the study based on the rationale provided in Section [3.5.1](#).

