CMV Surveillance	Arm A only: Surveillance for active disease must be conducted approximately every 4 weeks.

Assessment or Procedure	Explanation
Idelalisib pharmacokinetics (Arm A)	Recording of the date and actual clock time of the last prior subject self-administration of study drug (should be the prior evening dose); pre-dose collection of plasma sample for idelalisib pharmacokinetics (with recording of the date and actual clock time of the date and actual clock time of blood collection)
IWRS access	Access of IWRS to document subject visit and to obtain kit number(s)
Study Treatment Administration	
Study drug administration (Arm A)	Morning dose of idelalisib to be administered to the subject in clinic (with recording of the date and actual clock time of the study drug administration)
Pretreatment	Oral antipyretic, oral or IV antihistamine, and IV corticosteroid to be administered to the subject at the same time as idelalisib (Arm A) and ~30 to ~60 minutes prior to ofatumumab infusion
Ofatumumab infusion	Ofatumumab, 1000 mg (Arm A) or 2000 mg (Arm B) to be administered by intravenous infusion ~30 to ~60 minutes after pretreatment
Ofatumumab infusion severity and duration assessment	Worst severity of ofatumumab infusion reaction to be graded and total duration of ofatumumab infusion to be recorded. Perform final check of vital signs ~15 to 30 mins following the end of the infusion
Post-Treatment Procedures and Assessments	
Idelalisib pharmacokinetics (Arm A)	Post-dose collection of plasma sample for idelalisib pharmacokinetics at 1.5 hours after study drug administration (with recording of the date and actual clock time of blood collection)
Study drug dispensing (Arm A)	Dispensing of 12-week supply of idelalisib to the subject with instructions for self-administration at home

**Abbreviations:** β-HCG= beta human chorionic gonadotropin, AKT=AKT (a serine/threonine protein kinase), ALP=alkaline phosphatase, ALT=alanine aminotransferase, AST=aspartate aminotransferase, EQ-5D=EuroQoL Five-Dimension, FACT-Leu=Functional Assessment of Cancer Therapy-Leukemia, HRQL=health-related quality of life, GGT=gamma-glutamyltransferase, Ig=immunoglobulin, IWRS=interactive web response system, LDH=lactate dehydrogenase, mTOR=mammalian target of rapamycin, PI3K=phosphatidylinositol 3-kinase, CMV Surveillance=Arm A only: Surveillance for active disease must be conducted approximately every 4 weeks.

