Idelalisib administration in clinic (Arm A only)		X		X		X			X	X			X								
Premedication and ofatumumab administration		X	X	X	X	X	X	X	X	X	X	X	X								
Infusion reaction severity/duration assessment		X	X	X	X	X	X	X	X	X	X	X	X								
Idelalisib pharmacokinetics (Arm A only)		X		X		X			X	X			X								
Idelalisib dispensing/accounting (Arm A only)		X								X			X		X		X	X	X		
Radiology assessment (CT/MRI) b	X								X		X		X		X		X	X	X		
Bone marrow biopsy/aspirate c	X								X		X		X		X		X	X			
HBV DNA by PCR d						X			X	X	X	X	X		X		X	X			

Period	Screen	Treatment																	Follow-up		
Visit	1	2	3	4	5	6	7	8	9	10	11	12	13	14	15	16	17	18+	End of Study	30 day	Long-term
Week	-4	1	2	3	4	5	6	7	8	12	16	20	24	30	36	42	48	Q12 Weeks		Within +30 days	To +5 years
Study Day	Within -28 Days	1	8	15	22	29	36	43	50	78	106	134	162	204	246	288	330				
Visit Window			±2	±2	±2	±2	±2	±2	±2	±3	±3	±3	±3	±3	±3	±3	±3	±7			
Post-study CLL therapy																					X
Long-term follow-up																					X

- a After Visit 17 and 18, urine β-HCG to be performed every 6 weeks ±5 d (women of child-bearing potential only)
- b At screening, CT/ MRI may be performed within 6 weeks prior to start of randomization; CT or MRI imaging of neck, chest, abdomen, and pelvis can be performed within 1 week of the visit. CT/MRI assessments will continue until ~129 events have been observed in the study population
- c At baseline, to be performed at investigator discretion to determine extent of CLL involvement and bone marrow cellularity. Post-baseline, to confirm CR or PD; if the subject does not otherwise meet criteria for CR or if the nature of PD does not require bone marrow confirmation, it is not necessary to obtain a follow-up bone marrow biopsy/aspire.
- d Only subjects who are Hbc antibody positive and HBV DNA negative at screening. Subjects will be tested monthly for the duration of ofatumumab therapy and every 3 months thereafter for 1 year from the last dose of ofatumumab per Section 5.4.5.
- e After screening, CMV surveillance for active disease must be conducted approximately every 4 weeks for subjects in Arm A.

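### Two-weekly blood counts recommended for the first 6 months of idelalisib have no place in the visit schedule after Week 8

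*Protocol*

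**What the plan says.** Section 5.4.4 of the protocol sets the monitoring frequency: "All subjects should have their blood counts monitored at least every 2 weeks for the first 6 months of idelalisib treatment". The same paragraph makes two actions mandatory once a low neutrophil count (ANC) is found. At 0.5 to below 1.0 Gi/L, counts become weekly. Below 0.5 Gi/L, "idelalisib must be interrupted and blood counts monitored weekly until ANC is" back to at least 0.5 Gi/L.

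The synopsis sets the visits: "Clinic/laboratory visits will occur weekly for Weeks 1 through 8, every 4 weeks at Weeks 12, 16, 20, and 24, and every 6 weeks" from Week 24 to Week 48. Section 6.2 tells sites where to find what is done at them: "The specific study procedures to be conducted for each subject enrolled in the study are presented in tabular form in" Appendix 7, with the detail in the visit sections. The Appendix 7 row "Hematology/ serum chemistry" is marked at every numbered visit and at End of Study, and carries no footnote.

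Other tests in the same schedule are treated differently. Footnote a reads "After Visit 17 and 18, urine β-HCG to be performed every 6 weeks". Footnote e reads "After screening, CMV surveillance for active disease must be conducted approximately every 4 weeks for subjects in Arm A". The CMV row of Table 6-8 repeats the interval: "Surveillance for active disease must be conducted approximately every 4 weeks". The urine pregnancy row of Table 6-13 likewise adds a test 6 weeks after Visit 17.

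**The concern.** The safety text and the schedule give different frequencies for the same test, and sites book their work from the schedule. Where this protocol wants a test outside visits, it says so in a footnote and in the visit tables, so a site reading an unmarked haematology row has no reason to expect extra draws.

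At stake is the first detection of asymptomatic neutropenia in Arm A between Week 8 and Month 6. Both mandatory actions in Section 5.4.4 depend on a count showing the fall. If the count comes late, so do the weekly monitoring and the interruption.

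The protocol gives reason to take the risk seriously:

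- Section 5.4.4 reports treatment-emergent Grade 3 or 4 neutropenia, including febrile neutropenia, on idelalisib.
- The single-agent Phase 1 study (Section 1.3.5.2.1) recorded Grade 3 or higher neutropenia in 46 of 191 subjects (24%), with attribution to idelalisib called uncertain and no timing given.
- Arm A also receives ofatumumab through Week 24. For that drug Section 5.4.4 cites Grade 3 or higher neutropenia in 45 of 108 patients with normal baseline counts (42%).

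**Working it through.** The protocol states no figure to reproduce here. The check compares the scheduled haematology days with a 14-day maximum interval.

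**Inputs**

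- Maximum interval: 14 days, for the first 6 months of idelalisib (Section 5.4.4).
- Scheduled days from Week 8: 50, 78, 106, 134, 162, 204 (Appendix 7).
- Visit windows: ±2 days at Day 50, ±3 days at the later visits (Appendix 7).
- End of Month 6: not defined. Two readings are used: 24 weeks (24 × 7 + 1 = Day 169) and 26 weeks (26 × 7 + 1 = Day 183).

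**Formulas**

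- Nominal gap = next scheduled day − previous scheduled day.
- Longest gap = latest permitted next day − earliest permitted previous day. The shortest gap is the reverse.
- Delay beyond Section 5.4.4 = gap − 14.

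| Interval | Nominal gap | Shortest gap | Longest gap | Nominal delay | Longest delay |
|---|---|---|---|---|---|
| Day 50 to 78 | 28 | 75 − 52 = 23 | 81 − 48 = 33 | 14 | 19 |
| Day 78 to 106 | 28 | 103 − 81 = 22 | 109 − 75 = 34 | 14 | 20 |
| Day 106 to 134 | 28 | 131 − 109 = 22 | 137 − 103 = 34 | 14 | 20 |
| Day 134 to 162 | 28 | 159 − 137 = 22 | 165 − 131 = 34 | 14 | 20 |
| Day 162 to 204 (26-week reading only) | 42 | 201 − 165 = 36 | 207 − 159 = 48 | 28 | 34 |

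Every shortest gap exceeds 14 days, so no use of the windows satisfies Section 5.4.4. The weekly visits before Day 50 do satisfy it.

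**Counts without a slot.** Stepping 14 days from each visit gives Days 64, 92, 120 and 148 (Weeks 10, 14, 18 and 22). Day 176 (Week 26) is added on the 26-week reading, because 176 is before 183. On the 24-week reading it falls after Day 169 and drops out. The total is four or five.

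**Average rather than worst case.** Suppose onset is equally likely on any day of a 28-day gap and the low count persists until the next draw. The mean wait is then 28/2 = 14 days under the schedule and 14/2 = 7 days under Section 5.4.4, an average delay of about 7 days.

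**Footnotes.** Appendix 7 footnotes a to g cover pregnancy testing, imaging, bone marrow, HBV DNA, CMV, diarrhoea history and *Pneumocystis* prophylaxis. None covers blood counts.

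**The case against.** The strongest reply is that the two texts are compatible. Section 5.4.4 addresses sites directly, Appendix 7 does not forbid extra draws, and the delay is zero at a site that adds them. The frequency is worded as *should*, under a Section 5.4 heading that speaks of recommendations, while the weekly counts and the interruption are worded as *must*. The CMV and pregnancy footnotes use firmer language, so the absence of one for a recommended test could be deliberate. Neither comparator needs a between-visit draw in Weeks 8 to 24: CMV testing then coincides with the 4-weekly visits, and the extra pregnancy tests start after Visit 17. Section 6.2 also refers sites to a study manual, which is not at hand and may mention interim counts.

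On the clinical side, the 24% comes from a study at several dose levels in which 54 of 191 subjects had CLL. The combination study of this regimen (Section 1.3.5.2.2, 21 subjects) saw no clinically significant myelosuppression, and Section 5.4.4 itself says idelalisib lacks substantial myelotoxicity. The current protocol version postdates September 2014 (Section 1.3.1) and accrual was planned over 12 months (Section 9.5), so few subjects may still be in the window.

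Most of this stands as a limit on size. It does not remove the conflict. A recommended frequency for all subjects on idelalisib still has to reach the people who book the draws, and an unseen manual does not repair the protocol. The number still in the window cannot be settled from the document: the prophylaxis and CH50 rows, marked only from Visit 18, suggest few, while the CMV marks at Visits 6 to 17 point the other way.

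**Conclusion.** The concern holds. Between Week 8 and Month 6 the schedule provides counts at twice the recommended interval, and after Week 24 at three times. Four counts per Arm A subject on idelalisib are unscheduled on a 24-week reading of 6 months and five on a 26-week reading. First detection can come nominally 14 days late in the four intervals to Week 24, with a ceiling of 19 to 20 days. The nominal 28 days, at most 34, apply only to the Week 24 to 30 interval on the 26-week reading.

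These sizes assume a site that follows the schedule alone and a subject without symptoms that would prompt an earlier count. The efficacy analysis is untouched. The point should be fixed because it delays mandatory safety actions and is cheap to correct.

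**What to change.** Add a footnote to the Appendix 7 haematology row, modelled on footnote e: Arm A subjects on idelalisib have blood counts at least every 2 weeks through Month 6, with local laboratory counts permitted between visits. State whether Month 6 ends at Week 24 or Week 26. Put matching wording in the synopsis and in Tables 6-7 to 6-11. Table 6-12 (Weeks 30 and 42) needs no change.

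The cost is one footnote, edits to the synopsis and five tables, and four local blood counts per Arm A subject (five on the 26-week reading), all of which Section 5.4.4 already asks for. Cumulative blood volume is unlikely to be an obstacle: Section 6.4 gives about 1.7 mL/kg per average 6-week period against a limit of 7.0 mL/kg.
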